CLINICAL TRIAL PROTOCOL

SPACE 2

Stent-protected Angioplasty in Asymptomatic Carotid Artery Stenosis vs. Endarterectomy Two two-arm Clinical Trials

Clinical Trial Code:	SPACE 2
ISRCTN number:	ISRCTN 78592017
Clinical Phase:	Therapeutic confirmatory (Phase III)
Version:	Final (10.10.2008) Including Amendment 1 (25.09.2012)

CLINICAL TRIAL PROTOCOL SUMMARY

Title:

SPACE 2: Stent-protected Angioplasty in Asymptomatic Carotid Artery Stenosis vs. Endarterectomy. Two two-arm clinical trials

Phase: III**Sponsor:**

University hospital of Heidelberg represented by the
Director of Administration [name]
[name]
[contact]
[contact]
e-mail: [contact]

Principal Investigators**Coordinating Investigator (LKP):**

[name]. med. Dr. h.c. [name]
Department of Neurology; University of Heidelberg
[name]
[contact]; [contact]
e-mail: [contact]

Principal Co-Investigators

[name]. med. [name]
Department of Vascular Surgery, Klinikum rechts der Isar der Technischen
Universität München
[name]
[contact]; [contact]
e-mail: [contact]

[name]. med. [name]
Department of Neuroradiology
UKSH Campus Kiel
[name]
[name]
[contact]; [contact]
e-mail [contact]

Financing / Status of the Sponsor:

BMBF/DFG (HA 1394/5-1)
Co-financing by pharmaceutical industry

Indication:

Asymptomatic carotid artery stenosis (I65.2)

Trial Population:**Key inclusion criteria:**

- Sonographic identification of a $\geq 70\%$ stenosis of the extracranial carotid

artery in a patient without stroke or stroke-like symptoms attributable to the target stenosis within the previous 180 days.

- Written informed consent
- For women with childbearing potential, adequate contraception

Key exclusion criteria:

- Non-atherosclerotic origin of stenosis
- Stenosis related neurological symptoms within the previous 180 days

Objectives:

The trial has a 30-day safety endpoint and a composite primary efficacy endpoint (periprocedural and long-term events):

OLD: SPACE-2a: The primary hypothesis is the superiority of carotid artery stenting (CAS) and carotid endarterectomy (CEA) as compared to best medical treatment alone (BMT) with respect to the composite primary endpoint.

SPACE-2b: The primary hypothesis is that stent-protected angioplasty is not inferior to carotid endarterectomy with respect to the composite primary endpoint.

NEW: Two separate superiority-trials of interventions versus best medical treatment (BMT) are designed. The decision for one type of intervention is made (CEA = SPACE2a or CAS = SPACE2b) prior randomization. In both studies - SPACE2a and SPACE2b - the interventional treatment-groups (CEA and CAS) will be compared with BMT separately. In addition data from the CEA and CAS-groups will be compared in an explorative manner.

Trial Design :

OLD: Randomized, controlled, open, multi-centre, 3 parallel groups

NEW: Two parallel studies with a randomized, controlled, open, multi-centre design with two arms each

Sample Size:

OLD: To be allocated to trial (n = 3,640); To be analyzed (ITT) (n = 3,640)

NEW: To be allocated and analyzed in the overall trial (n = 3,272); to be allocated to SPACE2a (n=1,636) and to SPACE2b (n=1,636)

Statistical Analysis:

The primary analysis will be intention-to-treat (ITT). In addition, a per-protocol (PP) analysis will also be performed after exclusion of patients who did not finish therapy or other serious protocol violations

Safety: A non-inferiority design with a non-inferiority-margin of 1.5% will be used (following the strategy of second level of the efficacy endpoint).

Efficacy:

OLD: A hierarchical testing procedure is used to test both efficacy hypotheses.

Its first level consists of two tests on differences in event rates (Space-2a: CAS versus BMT and CEA versus BMT). Rates are compared by Chi²-test or a z-test (if losses to follow-up require the calculation of event rates and their standard errors by Kaplan-Meier-techniques).

If both tests show a significant result, the second level of the hierarchical testing procedure assesses non-inferiority of the event rates in the CAS/CEA groups (Space-2b) based on a one-sided 97.5% confidence interval under H₀ for the rate difference (H₀: rate_{CAS}-rate_{CEA} >= 0.025). The non-inferiority margin is set to 2.5%.

NEW: The primary analysis consists in testing the difference between intervention (CEA or CAS) and BMT with respect to the composite primary end point (Section

2.3). The comparison will use the Cox-PH model. The tests are performed on a 5% level. In addition an explorative comparison of the event rates in the CEA and the CAS groups will be done (Calculating a 95% confidence interval of the hazard rate for the primary endpoint between both treatments). In order to analyze the effect between these two interventional methods, an indirect treatment comparison will be performed.

Trial Duration and Dates:

Follow-up per patient: 5 years

First patient in to last patient out: 8 years (3-year-recruiting phase, 5-year-follow-up)

Total trial duration 9 years

Duration of treatment per patient: Stent-protected angioplasty and carotid endarterectomy are performed within 4 weeks of randomization. Best medical treatment continues throughout the follow-up period.

ABBREVIATIONS

AE	Adverse Event
BDSG	Bundesdatenschutzgesetz
BMBF	Bundesministerium für Bildung und Forschung
BMT	Best medical treatment
CAS	Carotid artery stenting
CEA	Carotid endarterectomy
CRF	Case Report Form
CTCAE	Common Toxicity Criteria for Adverse Events
CV	Curriculum Vitae
DBL	Data Base Lock
DFG	Deutsche Forschungsgemeinschaft
DMC	Data Monitoring Committee
DVP	Data Validation Plan
EC	Ethics Committee
EEC	Endpoint Evaluation Committee
ExC	Executive Committee
ECG	Electrocardiogram
GCP	Good Clinical Practice
ICH	International Conference on Harmonization of Technical Requirements for Registration of Pharmaceuticals for Human Use
ISF	Investigator Site File
ISRCTN	International Standard Randomized Controlled Trial Number
ITT	Intention To Treat
KKS	Coordination Center for Clinical Trials (Koordinierungszentrum für Klinische Studien)
LKP	Coordinating Investigator according to German law (Leiter der Klinischen Prüfung)
n.a.	not applicable
OE	Outcome Event
SAE	Serious Adverse Event
SC	Steering Committee
SDV	Source Data Verification
SUSAR	Suspected Unexpected Serious Adverse Reaction
TMF	Trial Master File

TABLE OF CONTENTS

Clinical Trial Protocol Summary	2
Abbreviations	5
Table of Contents	6
Flow Chart / Trial Schedule	9
1 Introduction	12
1.1 Scientific background	12
1.1.1 Evidence	13
1.1.2 Role of conservative treatment	13
1.1.3 Role of carotid endarterectomy	13
1.1.4 Role of carotid artery stenting	14
1.2 Trial rationale/ justification	14
1.3 Benefit / risk assessment	15
2 Trial Objectives and Endpoints	16
2.1 General aim / primary objective	16
2.2 Assessment of safety	16
2.3 Composite primary efficacy endpoint	16
2.4 Secondary and tertiary outcomes	17

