5.2 Screening and randomization

To qualify for this trial, patients must have met all above described inclusion and none of the exclusion criteria. Screening and randomization can be done at the same day, and randomization must be done within 14 days after screening, otherwise screening-examinations have to be repeated. The interventional therapy that will be tested vs. BMT has to be chosen by the treating physician and the patient prior to randomization. Following this decision patients will be assigned to SPACE2a or SPACE2b. Randomization between BMT and intervention is performed after the eligibility of a patient has been accepted by the involved discipline and after the patient has been examined from the study neurologist. Randomization will be done with an internet-based system provided by the data-center in Munich. Randomization will be stratified by an age-limit of 75years, providing the same numbers of instances per group in both age-cohorts. If the patient has been randomized to the interventional arm, treatment must be done within 4 weeks after randomization. Events occurring between randomization and treatment are counted within the allocated treatment group. Events between screening and randomization are not counted, but have to be noticed in preexisting condition in the CRF.

Before randomization following procedures has to be done:

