9.3 Definition of trial population to be analyzed

The primary analysis will be intention-to-treat (ITT). In addition, due to the nature of a non-inferiority study, a per-protocol (PP) analysis will also be performed. The PP includes all patients without major protocol deviations. The following are considered major protocol deviations:

- Not meeting one or more of the Inclusion Criteria and/or falling into one or more of the Exclusion Criteria
- Not finishing the allocated therapy (change of treatment group)
- Operation or Stenting done by an non-certified interventionalist or using non-certified material
- Endpoint event between randomization and treatment (if allocated to CEA or CAS)

In case of problems with the decision if a protocol violation is major, the Endpoint Evaluation Committee (see page 40) is responsible for the allocation; this will be done prior the unblinding of the data.

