9.4 Statistical methods

Biometric analysis will be defined in the statistical analysis plan which has to be authorized before closing the database by the biometrician, the sponsor, and the LKP.

OLD: Safety: The one-sided 97.5% confidence interval under H_0 for the difference of the event rates (rate in the CAS group – the rate in the CEA group) will be calculated. Non-inferiority is proven if the upper margin of this interval is less than 1.5%. This test has power of 90% if CAS shows a slight safety advantage compared to CEA (2.5% CAS versus 3% CEA). The power of the non-inferiority test is 80% in case of a slightly reduced risk in both procedures (CAS and CEA 2%).

Efficacy: In order to control the overall Type I error on the 5% level, a hierarchical testing procedure will be used. The first step of the procedure consists in a closed testing procedure for the difference between the three treatments. The tests are performed on a 5% level. If there are simultaneously significant differences between the pairs BMT and CEA as well as BMT and CAS on a 5% level, the hierarchical testing procedure enters step 2, otherwise there is no further statistical testing. Since superiority for CEA and CAS over BMT is not yet established in the studied population both tests need to be significant to allow the interpretation of step 2 in a clinically sensible way. Step 2 of the procedure consists in a non-inferiority test: The one-sided 97.5% confidence interval for the difference of the event rates (rate in the CAS group – the rate in the CEA group) will be calculated. Non-inferiority is proven if the upper margin of this interval is less than 2.5%.

In case of losses to follow up, the event rates and their standard errors will be calculated by Kaplan-Meier-techniques.

NEW:

Safety: If in the interim analysis the absolute rate of safety events (any stroke or death within 30 days after intervention) in the CEA-arm (for SPACE2a) or in the CAS-arm (for SPACE2b) with a confidence interval of 80% is higher than 3%, the DSMB can recommend stopping the trial. If the lower 80%-confidence-interval of the safety-event-rate is higher than 5%, the DSMB will recommend stopping the trial.

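### The summary still prescribes a 1.5% CAS–CEA non-inferiority test for safety that section 9.4 has superseded and that does not fit the two-trial design

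*Protocol*

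**What the plan says.** The protocol marks superseded text OLD and amended text NEW. In the summary's Statistical Analysis entry the efficacy paragraph carries both labels. The safety line just above it carries neither: "A non-inferiority design with a non-inferiority-margin of 1.5% will be used (following the strategy of second level of the efficacy endpoint".

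The second level is described in the summary only under OLD: "If both tests show a significant result, the second level of the hierarchical testing procedure assesses non-inferiority of the event rates in the CAS/CEA groups". It was the CAS versus CEA step of the three-arm hierarchy.

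Section 9.4 has two safety texts.
- The OLD text specifies the 1.5% test through "The one-sided 97.5% confidence interval under H_0 for the difference of the event rates" (CAS minus CEA), with a stated power of 90% at CAS 2.5% versus CEA 3% and 80% at 2% in both.
- The NEW text begins "If in the interim analysis the absolute rate of safety events (any stroke or death within 30 days after intervention) in the CEA-arm" and sets out when the DSMB can or will recommend stopping, using 80% confidence limits against 3% and 5%. It contains no non-inferiority test.

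Section 9.3, which is unlabelled, still justifies the per-protocol analysis "due to the nature of a non-inferiority study".

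Section 5.2 describes allocation after the amendment: "The interventional therapy that will be tested vs. BMT has to be chosen by the treating physician and the patient prior to randomization". Section 6.2 restricts the safety endpoint to patients randomised to CEA or CAS.

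**The concern.** Someone working from the summary and someone working from section 9.4 would carry out different safety analyses. The summary's version gives a formal verdict on whether CAS is non-inferior to CEA for 30-day stroke or death. The amended trial is not built to deliver that verdict: both substudies are superiority trials against BMT, and the procedure is now a choice made before randomisation. Selection of patients for one procedure or the other could create or hide a difference of 1.5 percentage points, and the confidence interval would not show it.

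Section 13.2 says the 30-day safety results will be published first. A pass or fail against a margin printed in the protocol would look pre-specified and confirmatory.

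**Working it through.** **Step 1. Which text is in force.**

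| Place | Label | Safety content |
|---|---|---|
| Summary, Statistical Analysis | none | 1.5% non-inferiority, modelled on the second level |
| Summary, Efficacy | OLD | defines the second level (CAS versus CEA) |
| 9.4, Safety | OLD | 1.5% non-inferiority, CAS minus CEA |
| 9.4, Safety | NEW | per-arm interim DSMB rule |
| 9.3 | none | non-inferiority as the reason for the per-protocol analysis |

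The unlabelled summary line rests on a step that no current text contains.

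**Step 2. Which contrast it would test.** With the endpoint confined to CEA and CAS patients (6.2), and the second level having been CAS versus CEA, the sentence can only mean CAS versus CEA.

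**Step 3. The status of that contrast.** The NEW text in the summary objectives, 2.1 and 3 makes CEA–CAS comparisons exploratory. Section 9.4 NEW says the same for the primary endpoint. Section 5.2 makes the procedure a choice before randomisation. Section 4.3 asks for a stenosis treatable by CEA or CAS, and 5.3.1 NEW needs only one discipline to confirm feasibility.

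**Step 4. Power (secondary).** Inputs: margin 0.015, one-sided 2.5% and the two rate scenarios (9.4 OLD); 1,505 and 1,550 per group (9.1 OLD); 818 per arm (4.1 NEW). Section 9.4 does not give the group size behind its power figures, so both old sizes were tried.

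Let d = pCAS − pCEA and SE = √{[pCAS(1−pCAS) + pCEA(1−pCEA)]/n}.
- (a) Unpooled: power = Φ((0.015 − d)/SE − 1.96)
- (b) Continuity-corrected: power = Φ((0.015 − d − 1/n)/SE − 1.96)
- (c) Variance restricted under H0, which suits the protocol's wording of the interval: power = Φ((0.015 − d − 1.96·SE0)/SE). SE0 uses rates constrained to differ by 0.015: 2.995% and 1.495% at 2%/2%; 3.743% and 2.243% at CAS 2.5%/CEA 3%.

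Reproducing the stated 80% by (b) at n = 1,505 and 2%/2%: SE = √(0.0392/1,505) = 0.005104; (0.015 − 0.000664)/0.005104 − 1.96 = 0.849; Φ = 80.2%.

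The same at n = 818: SE = √(0.0392/818) = 0.006923; (0.015 − 0.001222)/0.006923 − 1.96 = 0.030; Φ = 51.2%.

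| n per group | Rates CAS/CEA | (a) | (b) | (c) | Stated |
|---|---|---|---|---|---|
| 1,505 | 2%/2% | 83.6% | 80.2% | 80.7% | 80% |
| 1,505 | 2.5%/3% | 91.9% | 90.0% | 90.6% | 90% |
| 1,550 | 2%/2% | 84.7% | 81.5% | 81.9% | 80% |
| 1,550 | 2.5%/3% | 92.6% | 90.9% | 91.4% | 90% |
| 818 | 2%/2% | 58.2% | 51.2% | 53.8% | – |
| 818 | 2.5%/3% | 69.6% | 64.2% | 66.8% | – |

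Formulas (b) and (c) reproduce the protocol's figures within two points. Formula (a) overshoots the 80%.

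**The case against.** The strongest reply is that the body of the protocol is clear. The amendment calls CEA versus CAS exploratory in several places, bases the sample size on efficacy against BMT, and has dropped the safety test from 9.4. On that view the summary line is a leftover that nobody would act on, and the power of a superseded test is hypothetical. Part of this stands: the mismatch with the design is the main point, and power is secondary. But the leftover is the only formal final safety test in the current text, and the summary is where many readers look.

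Four stronger readings are tempting, and the documents do not support them.

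- *A reader might infer that no CAS patient was randomised against a CEA patient.* Section 3 dates the start of recruitment to October 2008, and the amendment is dated September 2012. Patients enrolled under the three-arm design were randomised between the two procedures. Their number is not given.
- *A reader might infer that no BMT comparison is available for 30-day events.* Section 6.1 defines 30-day endpoints for BMT patients, and 6.3.1 includes 30-day stroke or death in the primary endpoint for all arms. An indirect comparison, the method named for CEA versus CAS, is therefore possible. It would not rescue the power. If the 30-day BMT rate is assumed to be p, SE = √{[0.0392 + 2p(1−p)]/818}, and formula (a) at 2%/2% gives about 54% for p = 0.2% and 42% for p = 1%.
- *A reader might quote a power of 58%, down from about 85% and 93%.* These come from the unpooled formula, the last two at 1,550 per group. The protocol states 80% and 90%, and the formulas that match it give lower values at 818.
- *A reader might take 9.4 NEW as the replacement final safety analysis.* It is an interim rule with an 80% interval. Deleting the summary line and nothing more would leave no final safety analysis stated.

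**Conclusion.** The plan is wrong as written on this point. Followed literally, the summary requires a non-inferiority verdict on 30-day safety between CAS and CEA. That verdict depends on a deleted step, conflicts with 9.4 NEW and with the exploratory status of the comparison, and for patients enrolled since the amendment lacks randomisation between the groups. Section 9.3 carries the same remnant.

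The loss of power is real but secondary: about 51–58% at 2%/2% and 64–70% at CAS 2.5% versus CEA 3%, against the stated 80% and 90%. The ranges reflect the choice of variance formula. They assume 818 patients in each intervention arm, a one-sided 2.5% level and a direct unadjusted comparison. Bias from choice of procedure is not included, and the documents give no figure for it. The primary efficacy tests against BMT are unaffected.

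**What to change.** - Delete the non-inferiority sentence from the summary's safety entry and the non-inferiority reason from 9.3. The per-protocol analysis can stay as an additional analysis without that reason.
- State in both the summary and 9.4 that the final safety analysis is the 30-day rate of any stroke or death in each intervention arm with its confidence interval, at a named level. Keep it separate from the interim DSMB rule.
- Label any CAS–CEA contrast on safety exploratory, with no non-inferiority conclusion.
- Check the summary, 9.3 and 9.4 against each other once this is done.

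The cost is a few sentences, with no new data and no change in sample size. What is given up is a confirmatory CAS–CEA safety claim that the amended design cannot support.

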15	Declaration of Investigator	51
16	References	52
17	Appendices	54

FLOW CHART / TRIAL SCHEDULE

Figure 1: Trial flow chart and visit plan (Old)

[figure not shown]
[figure not shown]

Figure 1: Trial flow chart and visit plan (**NEW**)

	Screening	Randomization	CAS/CEA	D1 ^b	D30	M6	A1	A2	A3	A4	A5
Informed consent	X	X									
Ultrasound	X			X	X	X	X	X	X	X	X
ECG	X			X							
Risk factor screening using a standardized questionnaire	X			X	X	X	X	X	X	X	X
Modified Rankin Score	X			a	a	a	a	a	a	a	a
NIH Stroke Scale	X			a	a	a	a	a	a	a	a
Co-medication	X			X	X	X	X	X	X	X	X
Event-Screening:	X			X	X	X	X	X	X	X	X
• Any stroke				X	X		X		X		X
• Ipsilateral ischemic stroke				X	X	X	X	X	X	X	X
• Death from any cause					X		X		X		X
• Vascular death					X		X		X		X
• Myocardial infarction					X						
• Technical failure			X								
Adverse Events			X	X	X	X	X	X	X	X	X

a: only in case of outcome events; b: only if randomized to CEA or CAS

1 INTRODUCTION

1.1 Scientific background

Treatment of individuals with asymptomatic carotid artery stenosis is handled controversially. Surgery for asymptomatic and symptomatic carotid artery bifurcation stenosis ranks among the most frequent surgical procedures worldwide. For Germany about 25,000 procedures are performed every year. The superiority of carotid endarterectomy (CEA) compared to medical treatment in symptomatic carotid disease (in patients, who already had stroke or TIA on the side of the stenosis) is established, provided that the surgical procedure can be done with a perioperative morbidity and mortality of less than 6% [6]. The advantage of CEA for asymptomatic patients (those, who did not have a previous cerebrovascular ipsilateral event) is less well established. There is a mild superiority of this intervention compared with standard medical therapy, provided that the operation can be done with the perioperative morbidity and mortality of less than 3%. Even then, about 20 patients have to be treated to prevent one stroke over a period of 5 years, which also causes doubts about the cost effectiveness of this intervention [8].

Recently, for both symptomatic and asymptomatic carotid artery stenoses, an alternative treatment, carotid stenting (stent-protected angioplasty, CAS) has been developed. This treatment is used frequently in both, symptomatic and asymptomatic patients. However, up to today, no prove of superiority or non-inferiority of carotid artery stenting for symptomatic stenosis has been demonstrated [20, 22].

In the last decade, major advantages in medical primary prevention of cerebrovascular and cardiovascular disease have been accomplished. Specifically, treatment of hypertension with modern antihypertensive drugs such ACE inhibitors or ARBs, partially in combination with diuretics and the use of statins have shown significant risk reduction for both cerebrovascular and cardiovascular events [1, 14]. In addition, life style modification, smoking cessation and individualized antiplatelet therapy may also have an impact on the event rate in so far asymptomatic patients. The control groups in the large trials for asymptomatic carotid artery disease (ACAS and ACST) originate from more than a decade ago and, for the major part, have not received a medical primary prevention strategy that would now be considered standard according to current national and international guidelines [18]. Therefore, for asymptomatic carotid artery

disease, it seems adequate and timely, to compare state of the art medical prevention with the interventional therapies. For that reason initially a three-arm trial with a hierarchical design was chosen. On the first level, a superiority trial of intervention (CAS or CEA) versus state of the art conservative treatment is designed. In case of superiority of the interventions, a non-inferiority endpoint will be tested between CAS and CEA. After some years problems with this study design became obvious, thus the design was modified to two parallel two-arm trials.

